10. LABORATORY CONSIDERATIONS

Blood and urine samples will be obtained at the first visit in the ED and during the 30 day follow-up visit in the Urology clinic. Up to 10 ml of blood will be drawn for laboratory assessment of CBC, BMP, and the coagulation panel.

The samples for standard of care testing will be sent to the laboratory at Ben Taub General Hospital. After tests are completed, any remaining samples will be destroyed per laboratory's Standard Operating Procedures.

No cell lines will be developed. If a subject withdraws, the samples will have already been destroyed; therefore, the subject will not be able to have the samples returned to them.

Subjects may see and get a copy of their research related health information. The research doctor may be able to provide subjects with part of their information while the study is in progress and the rest of their information at the end of the study.

11. SAMPLE SIZE

The primary outcome measure is spontaneous stone passage. The proportion of patients who spontaneously pass the stone within 30 days will be compared between the mirabegron and placebo groups using Fisher's exact test. Previous research suggests that about 50% of subjects in the placebo group will have a spontaneous stone passage. A sample size of 45 subjects per group will provide 80% power to detect a 0.30 unit difference in proportions using Fisher's exact test assuming alpha=0.05 and half of the patients in the placebo group have spontaneous stone passage. Therefore, a total of 104 subjects will be enrolled into this study to allow for 15% attrition.

12. STATISTICAL CONSIDERATIONS

The primary analysis will evaluate the difference in the proportion of subjects who successfully pass their ureteral stone between subjects who received mirabegron and placebo. This analysis will provide information regarding the efficacy of mirabegron to improve stone passage rates for patients undergoing expectant stone management.

The secondary analyses will involve a multivariable analysis to compare the difference in pain during passage and pain with a ureteral stent in place. This may include co-variates such as age, gender, location of ureteral stone, prior history of ureteral stones, pain medication used during expectant management, and stone size.

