9. PROCEDURES

Visit 1 – Emergency Department

In the ED, the subjects will receive a full history and physical, blood tests (including CBC and BMP), urinalysis and culture, urine pregnancy test, CT scan or Ultrasound/KUB of the abdomen

and pelvis, and KUB as part of standard of care for ureteral colic. The radiology department will note on all imaging the largest diameter of the stone and the Hounsfield units. Research study staff will screen potential subjects in the ED by reviewing their charts and will obtain written and verbal consent (in Spanish when necessary) from subjects who meet all inclusion and exclusion criteria. Baseline data, including demographics, medical and surgical history, and current medications, will be collected before randomization.

Each subject will be assigned a unique, consecutive three-digit identification number (i.e., 001, 002...). The study number will be utilized for identification of the subject throughout the study. The clinical study coordinator of the trial will maintain the code that links the name of the participant to their study identification number. The study coordinator will maintain the code in a secured cabinet and the code will be kept confidential. Only the clinical study coordinator and Principal Investigator (PI) can access and view the codes.

Subjects will be asked to complete the Wong-Baker FACES pain scale (available with validated Spanish translation as well). Subjects will be discharged from the ED with a (1) 60 day prescription for the study drug (mirabegron or placebo) (2) urine strainer (3) 60 day log for recording medication adherence, narcotic/analgesic usage, and ureteral pain. Subjects will be instructed to take one pill per day beginning immediately and continuing until they have completed all pills or until they have been instructed to discontinue by the study staff.

Subjects will be provided instructions for use of the urine strainer and collection of any stone or stones that may be passed. They will be instructed to bring any stones that have been passed to the next clinic visit.

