Subjects will follow-up in the Harris Health Urology Clinic approximately 30 days after Visit 1. Subjects will provide a blood sample for a CBC, BMP, coagulation studies (PT/INR/PTT), a urine sample for a urinalysis and culture, urine pregnancy test, and have their blood pressure taken, as per standard of care. Subjects will also undergo a CT or KUB plus renal ultrasound at the Harris Health Radiology Department to radiologically identify the status of their ureteral stone, as per standard of care.

| In the Urology Clinic, staff will perform a brief history and physical, review clinical imaging, observe any stones that the subject has collected, and determine whether or not the subject has passed their ureteral stone. Clinical and research staff will assess blood pressure, ureteral pain, pain medication and pain score log compliance, medication/strainer compliance, and adverse events using the adverse event checklist. Subjects will be asked to bring in their medication bottles at this visit to assess medication compliance. Subjects with persistent ureteral stones will be scheduled for ureteroscopy with laser lithotripsy and ureteral stent placement. These subjects will continue the study drug and strain their urine. Subjects will be provided additional study drug if necessary and instructed to continue until Visit 4, regardless of if they believe they passed their stone or not. They will be asked to bring the study drug bottle and any collected stones upon their return to Visit 3.

Subjects who have passed their stone will discontinue the study drug and exit the study.

Visit 3 – Ureteroscopy (14 days ± 5 days post-Visit 2)

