Subjects who have failed the expectant management period as determined on Visit 2 will undergo ureteroscopy with laser lithotripsy approximately 14 days after Visit 2. Blood pressure will be checked prior to the procedure. Stone fragments will be collected for composition analysis. All subjects will be stented using the preferred 6-French Boston Scientific Contour Injection Ureteral Stent Set that has been appropriately sized for each patient. If this particular catheter cannot be used, any 6-French catheter is preferred, but any ureteral catheter may be utilized during this visit. The string will not be removed from the ureteral stent to facilitate easier removal later. In subjects for whom the ureteroscope cannot successfully be passed into the ureter after reasonable attempts, the surgeon will place a ureteral stent and the subject will remain on the trial until their ureteral stent has been in 1 week or until Visit 4. Subjects will receive 10 days of ciprofloxacin, Tylenol #3, phenazopyridine, per standard of care. Subjects will not be prescribed alpha-adrenergic blockers or anticholinergics.

Clinical and research staff will assess blood pressure, ureteral pain, pain medication and pain

score log compliance, medication/strainer compliance, and adverse events using the adverse event checklist.

They will be asked to bring the study drug bottle upon their return to the clinic at Visit 4. It is possible that some patients will pass their stone between visit 2 and visit 3. If the patient has physically seen the stone pass or has collected the stone, they will exit the study; otherwise, they will proceed with a diagnostic versus therapeutic ureteroscopy with stent placement.

Visit 4 – Removal of Ureteral Stent (7 days ± 3 days post- Visit 3)

Subjects will return the Harris Health Urology Clinic approximately 7 days after ureteroscopy to remove their ureteral stent. In the Urology Clinic, staff will perform a brief history and physical, including blood pressure, per standard of care. Subjects will complete the USSQ. Stent pain, medication compliance, and medication-related adverse events, if any, will be assessed. Subjects will be asked to return any unused study drug and the study drug bottle at this visit. For subjects in whom the ureteroscope could not be passed and a stent was left in place, this visit will be a return to the operating room for completion ureteroscopy or stent removal, as clinically indicated.

Early Completion of the Trial Period

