13. DATA ANALYSIS

Patient demographics and clinical characteristics will be summarized by means with standard deviations, medians with minimum and maximum values, or frequencies with percentages. Summary statistics will be stratified by treatment group. No univariable analysis will be completed in this randomized clinical trial.

The primary analysis will compare the proportion of subjects with spontaneous stone passage within 30 days between study groups using Fisher's exact test. Statistical significance will be assessed at the 0.05 level (two-sided). A logistic regression model will also be used to estimate the odds ratio for spontaneous stone passage in the mirabegron group versus the placebo with a 95% confidence interval.

A multiple logistic regression model, adjusting for treatment group, will also be used to test for significant associations between spontaneous stone passage and patient demographics or clinical characteristics. Parameter estimates significant at the 0.05 level will be included in the final multiple regression model. No adjustments will be made for multiple hypothesis testing.

A secondary objective of this study is to compare pain measures between treatment groups. The Wong Baker FACES pain scale will be measured daily for each patient. A general linear mixed model will be used to compare pain scores between treated and placebo groups. The model will include fixed effects for treatment group, time (discrete) and a group-time interaction term. The matrix of correlated residual terms will assume an unstructured format. This model will account for the correlation between repeated measures within the same subject and will allow for all available data to be included in the model.

Missing data will not be imputed. Model fit will be assessed using influence diagnostics and residual analysis. Data transformations (e.g., natural logarithm) will be used if departure from model assumptions is evident. The model will also be used to explore associations between pain scores and demographic and clinical characteristics, adjusting for treatment group and time.

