The USSQ will be observed in patients who require surgical intervention, and will be observed during study visit 4. A general linear model will be used to compare USSQ pain scores between the treated and placebo groups. The model will also be used to explore associations between pain scores and demographic or clinical characteristics adjusting for treatment group. Secondary analyses will be assessed at the 0.05 level (two-sided) without adjusting for multiple comparisons.

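### Section 12 leaves open adjusting the pain comparisons for post-randomisation analgesic use; the stratifiers are fixed in neither pain model, and the stent-pain test in surgical patients is not labelled conditional on surgery

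*Combined protocol and SAP*

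**What the plan says.** Section 12 describes one multivariable secondary analysis to compare pain during passage and pain with a stent. On covariates it says: "This may include co-variates such as age, gender, location of ureteral stone, prior history of ureteral stones, pain medication used during expectant management". Stone size completes that list. Analgesic use is recorded at home: at ED discharge, with the study drug, subjects receive a "60 day log for recording medication adherence, narcotic/analgesic usage, and ureteral pain" (Section 9), and Section 7 has patients recording narcotic use and pain scores during follow-up.

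Section 13 gives two models:
- Daily pain, a mixed model: "The model will include fixed effects for treatment group, time (discrete) and a group-time interaction term".
- Stent pain: "A general linear model will be used to compare USSQ pain scores between the treated and placebo groups". The population is restricted: "The USSQ will be observed in patients who require surgical intervention, and will be observed during study visit 4".

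For both, Section 13 adds: "Secondary analyses will be assessed at the 0.05 level (two-sided) without adjusting for multiple comparisons".

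Section 8 stratifies randomisation by stone size (5 mm cut) and by upper v lower ureter. Neither factor is a fixed term in either pain model. Patients whose stone passes do not reach the USSQ. At Visit 2, "Subjects who have passed their stone will discontinue the study drug and exit the study". Between Visits 2 and 3, "If the patient has physically seen the stone pass or has collected the stone, they will exit the study". Sections 3, 7 and 13 all state that stent pain is assessed only in patients who have surgery.

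**The concern.** There are three linked gaps.

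1. Section 4 of the argument is the drug's mechanism: the Background hypothesises that it relieves ureteral pain, so analgesic use in the expectant period may be a consequence of treatment. Adjusting for it no longer estimates the effect of assignment on recorded pain. Section 12 permits the adjustment, the Section 13 models do not contain it, and nothing says which governs or when that is decided. The choice could be made after the data are seen.
2. Randomisation was stratified on two factors, but using them in the pain comparisons is optional. This applies to the mixed model as much as to the USSQ model.
3. The USSQ population is closely tied to failure on the primary outcome, which the drug is meant to change. Stent pain is in the study title, so an unqualified p-value invites reading as a randomised test.

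The primary Fisher test is untouched.

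**Working it through.** **Step 1. The plan's own figure.** Section 11 gives 45 per group for 80% power at 50% v 80% passage (Fisher, alpha 0.05). Exact enumeration at 45 per group gives 81.5%. Enrolment: 90 × 1.15 = 103.5, so 104, or 52 per arm. The plan gives no figure for either pain comparison. Every effect and correlation in Steps 2, 4, 5 and 6 is an assumption.

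**Step 2. What analgesic adjustment can do.** This is a one-time-point sketch, not the daily model. Within-arm latent pain has SD 2 and the drug effect on it is −1.0. Analgesic use M = 0.5 × pain + noise (SD s). Recorded pain = pain − kM.
- Unadjusted difference: −1.0 + 0.5k.
- Within-arm slope of pain on M: (0.5 × 4)/(0.25 × 4 + s²) = 2/(1 + s²).
- Adjusted difference: −1.0 + 0.5 × 2/(1 + s²) = −s²/(1 + s²), whatever k is.

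| s = 1 | k = 0 | k = 0.6 | k = 1 | k = 1.5 |
|---|---|---|---|---|
| Unadjusted | −1.00 | −0.70 | −0.50 | −0.25 |
| Adjusted | −0.50 | −0.50 | −0.50 | −0.50 |

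The adjusted value is −0.20 at s = 0.5 and −0.80 at s = 2. At s = 1, adjustment halves the estimate, leaves it unchanged or doubles it. At k = 1.5 the adjusted figure is the closer one to −1.0. A second sketch, with shared severity, a direct effect of −0.5 and an analgesic effect of −0.2 on pain, gave −0.34 to −0.46 unadjusted and −0.10 to −0.42 adjusted.

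**Step 3. Size of the stented groups.** 52 × 0.50 = 26 v 52 × 0.20 = 10.4, so about 26 v 10. With 45 per arm: 22.5 v 9, so about 22 v 9. Both are approximate, since some late passers exit before ureteroscopy. The difference detectable with 80% power (noncentral t, unit SD) is 1.07 SD for 26 v 10 and 1.15 SD for 22 v 9.

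**Step 4. Selection.** Let D be a stone's standardised difficulty of passage and r its correlation with stent pain. Bias = r × (mean D among mirabegron failures − mean D among placebo failures); positive counts against mirabegron.
- Threshold model, mean D among failures = φ(z_p)/(1 − p): 1.400 at 80% passage and 0.798 at 50%, a difference of +0.602.
- Rescue model (placebo fails if D > 0; the drug rescues a would-be failure with logit a + bD, with a set to give 80% passage): +0.352, +0.208, 0, −0.189, −0.309 at b = −2, −1, 0, +1, +2.
- Equal passage in the two arms: 0 in both models.

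At r = 0.5 the bias runs from 0.5 × 0.602 = 0.30 SD against mirabegron to 0.5 × 0.309 = 0.15 SD in its favour.

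**Step 5. Effect on the test (26 v 10, no true effect on stent pain).**

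| Bias against mirabegron (SD) | r, threshold model | False harm (nominal 2.5%) | Two-sided error (nominal 5%) |
|---|---|---|---|
| 0.06 | 0.1 | 3.6% | 5.3% |
| 0.18 | 0.3 | 6.8% | 7.6% |
| 0.30 | 0.5 | 12.0% | 12.3% |

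In the other direction, biases of 0.03, 0.09 and 0.15 SD give false relief of 3.0%, 4.2% and 5.8%. Power for a true 1.07 SD benefit runs from 52% (bias 0.30 against) to 89% (0.15 in favour). At 50% v 60% passage, r = 0.5 and the threshold model, the groups are about 26 v 21, the bias is 0.5 × 0.168 = 0.08 SD and two-sided error is about 5.9%.

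**Step 6. What stratifier adjustment removes.** If size and location explain 10%, 25% or 50% of difficulty, adjusting for them removes about 3–4%, 9–11% or roughly a quarter of the bias.

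**The case against.** The strongest defence is that Section 12 is an overview in permissive language and Section 13 holds the operative models. Section 13 also has a step that explores associations between pain and patient characteristics, and the Section 12 list could feed only that. This does not hold: Section 12 attaches the list to the analysis that compares pain, which is the treatment comparison. But the wording is only permissive, and nothing says that an adjusted result would replace the Section 13 contrast.

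Several other objections stand:
- A reader might infer that the plan overlooked its stratifiers. It did not: Section 12 lists both location and stone size, as options. The gap is that they are not fixed, and it is not specific to the USSQ.
- A reader might infer that the surgical restriction is hidden. Sections 3, 7 and 13 state it, and it cannot be avoided, since only stented patients can report stent pain. What is missing is the consequence for inference.
- The 12% needs a deterministic threshold, the full 30-point effect and r = 0.5 together. Milder assumptions leave error near 5%.
- Fixing the stratifiers is weak protection against selection, as Step 6 shows.
- Age, gender and prior stone history are baseline variables, and there is no case against them.

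**Conclusion.** The point holds, for secondary endpoints only. The plan leaves open a post-randomisation covariate that changes what the pain comparison estimates, fixes the stratifiers in neither pain model, and tests stent pain at 0.05 in a subset selected by an outcome the drug is meant to change, without saying so.

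Three stronger readings are tempting and unsupported. The first is that analgesic adjustment always weakens or worsens the estimate: Step 2 shows it can move either way, so the fault is the open choice between two contrasts. The second is that the USSQ comparison is biased against mirabegron: the direction depends on which stones the drug helps and on how difficulty of passage relates to stent pain, and the documents give neither. The third is that the stent-pain test is invalid whatever happens: in the models tried, the bias is zero if passage is equal, and also zero if rescue is unrelated to difficulty (b = 0).

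The two-sided error of about 12% is the extreme of the scenarios tried, not an expected value. The group sizes of 26 v 10 or 22 v 9 rest on the plan's own passage rates.

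**What to change.** - **Section 12:** delete the analgesic-use item from the covariate list, so that the treatment comparisons use baseline covariates only. Summarise analgesic use by arm descriptively from the diary. Age, gender and prior stone history need no change.
- **Section 13, both pain models:** include stone size (≤5 v >5 mm) and location (upper v lower), coded as randomised, as fixed terms in the mixed model and in the USSQ model.
- **Section 13, USSQ:** report the number stented and their stone characteristics by arm. Report the contrast as exploratory and conditional on surgery, and note that stratifier adjustment improves precision but removes only a small part of any selection bias.

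The cost is SAP wording and one extra table, with no new data. The downsides are two degrees of freedom spent in about 31 to 36 stented patients (22 + 9 to 26 + 10) and a weaker stent-pain claim.

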13. DATA ANALYSIS

Patient demographics and clinical characteristics will be summarized by means with standard deviations, medians with minimum and maximum values, or frequencies with percentages. Summary statistics will be stratified by treatment group. No univariable analysis will be completed in this randomized clinical trial.

The primary analysis will compare the proportion of subjects with spontaneous stone passage within 30 days between study groups using Fisher's exact test. Statistical significance will be assessed at the 0.05 level (two-sided). A logistic regression model will also be used to estimate the odds ratio for spontaneous stone passage in the mirabegron group versus the placebo with a 95% confidence interval.

A multiple logistic regression model, adjusting for treatment group, will also be used to test for significant associations between spontaneous stone passage and patient demographics or clinical characteristics. Parameter estimates significant at the 0.05 level will be included in the final multiple regression model. No adjustments will be made for multiple hypothesis testing.

A secondary objective of this study is to compare pain measures between treatment groups. The Wong Baker FACES pain scale will be measured daily for each patient. A general linear mixed model will be used to compare pain scores between treated and placebo groups. The model will include fixed effects for treatment group, time (discrete) and a group-time interaction term. The matrix of correlated residual terms will assume an unstructured format. This model will account for the correlation between repeated measures within the same subject and will allow for all available data to be included in the model.

Missing data will not be imputed. Model fit will be assessed using influence diagnostics and residual analysis. Data transformations (e.g., natural logarithm) will be used if departure from model assumptions is evident. The model will also be used to explore associations between pain scores and demographic and clinical characteristics, adjusting for treatment group and time.

The USSQ will be observed in patients who require surgical intervention, and will be observed during study visit 4. A general linear model will be used to compare USSQ pain scores between the treated and placebo groups. The model will also be used to explore associations between pain scores and demographic or clinical characteristics adjusting for treatment group. Secondary analyses will be assessed at the 0.05 level (two-sided) without adjusting for multiple comparisons.

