1. BACKGROUND

Kidney stone passage down the ureter into the bladder often results in severe abdominal pain called ureteral colic. Ureteral colic is a common presenting symptom in emergency departments (ED).

Approximately 550,000 episodes of ureteric colic are seen in ED in the United States per year costing nearly \$3 billion.¹ The current standard of care for ureteral stone passage involves hydration and pain control as approximately 47-80% of stones will pass within approximately 4 weeks, depending on size and location.² Patients who cannot achieve spontaneous stone passage or have a subsequent complication (including recurrent pain, compromised renal function, or infection) often require surgical therapy, typically either with extracorporeal shock wave lithotripsy or ureteroscopy. Two decades ago, the first randomized trial demonstrating the potential efficacy of a calcium channel blocker (nifedipine) for medical expulsive therapy of ureteral stones was performed.³ Subsequently, tamsulosin, a selective alpha-1a antagonist, has also been demonstrated as a potentially useful agent for medical expulsive therapy (MET) in randomized trials.⁴ Over the past decade, off-label MET has become more commonplace. However, the strength of findings from randomized trials is weak due to variability in quality and power of study design.

In 2015, a large multi-center randomized placebo-controlled trial (SUSPEND Trial) included 1167 patients and compared the efficacy of nifedipine and tamsulosin for the reduction in surgical therapy in patients passing ureteral stones within 4 weeks after randomization.⁵ This trial demonstrated that both nifedipine and tamsulosin were ineffective for MET and were associated with an increase in adverse effects (AE) compared to placebo. These findings suggest that current off-label therapy with calcium-channel blockers and alpha-blockers may be ineffective and inappropriate. Because ureteral stones remain an important and expensive medical problem, identification of other potential agents for MET may reduce the frequency of serious complications and necessity of surgical intervention as well as improve patient- centered outcomes.

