8. RANDOMIZATION

Study participants will be randomized to the treated arm (mirabegron 50 mg orally once every 24 hours starting immediately) or placebo in a 1:1 ratio using a randomized block design, stratified by stone size (≤ 5 mm versus > 5 mm) and location (upper versus lower ureter). The randomization will be implemented through a database with software designed by the Director of Research Informatics at the Baylor College of Medicine's (BCM) Dan Duncan Institute of Clinical and Translational Research. It will be a HIPPA-compliant secure database accessible via internet.

Each randomly assigned participant will be given 60 capsules of trial medication (over-encapsulated mirabegron or placebo) supplied by Astellas Pharm US, Inc. and dispensed by the Harris Health System Pharmacy. Both Astellas Pharm US, Inc. and Harris Health Pharmacy will have no further involvement in the trial, ensuring that participants, clinicians, and trial personnel remained unaware of the allocated group.

Justification:

Two decades ago, the first randomized trial demonstrating the potential efficacy of a calcium channel blocker (nifedipine) for medical expulsive therapy of ureteral stones was performed.³ Subsequently, tamsulosin, a selective alpha-1a antagonist, has also been demonstrated as a potentially useful agent for MET in randomized trials.⁴ Over the past decade, off-label MET has become more commonplace. However, the strength of findings from randomized trials is weak due to variability in quality and power of study design.

In 2015, a large multi-center randomized placebo-controlled trial (SUSPEND Trial) included 1167 patients and compared the efficacy of nifedipine and tamsulosin for the reduction in surgical therapy in patients passing ureteral stones within 4 weeks after randomization.⁵ This trial demonstrated that both nifedipine and tamsulosin were ineffective for MET and were associated with an increase in adverse effects compared to placebo. These findings suggest that current off-label therapy with calcium-channel blockers and alpha-blockers may be ineffective and inappropriate. Because ureteral stones remain an important and expensive medical problem, identification of other potential agents for MET may reduce the frequency of serious complications and necessity of surgical intervention as well as improve patient-centered outcomes.

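### Randomisation is stratified by stone size and location, but no planned analysis of stone passage is certain to use the strata; the plan is valid, and using them is a low-cost improvement

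*Combined protocol and SAP*

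**What the plan says.** - Section 8 allocates 1:1 "using a randomized block design, stratified by stone size" (5 mm or less against more than 5 mm) and by location (upper against lower ureter), which makes four strata.
- Section 1 treats both factors as prognostic: a range of 47-80% of "stones will pass within approximately 4 weeks, depending on size and location".
- Section 11 sizes the trial on Fisher's exact test with 50% passage on placebo: "A sample size of 45 subjects per group will provide 80% power to detect a 0.30 unit difference in proportions". It adds that "a total of 104 subjects will be enrolled into this study to allow for 15% attrition".
- Section 13 names the same test for the primary analysis, two-sided at 0.05: "The primary analysis will compare the proportion of subjects with spontaneous stone passage within 30 days between study groups". No strata are mentioned.
- Section 13 continues: "A logistic regression model will also be used to estimate the odds ratio for spontaneous stone passage in the mirabegron group versus the placebo". No covariates are listed, and the text does not say whether the model is adjusted.
- A separate multiple logistic model in Section 13 "will also be used to test for significant associations between spontaneous stone passage and patient demographics or clinical characteristics". Terms stay in the final model only if significant at 0.05.
- Section 12 lists stone size and location as covariates, but for the secondary pain analyses and only as options: "This may include co-variates such as age, gender, location of ureteral stone".

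**The concern.** The two factors were thought important enough to balance at randomisation, yet nothing guarantees them a place in any analysis of the primary endpoint. They can reach a stone-passage model only by passing a significance screen.

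Type I error is not at stake. A pooled test after stratified randomisation does not inflate it, and becomes more conservative as the strata become more prognostic. Two other things are at stake: power at the fixed sample size, and whether the trial will report a treatment effect adjusted for the factors it chose to balance.

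**Working it through.** **1. The plan's own figure.** Inputs from Sections 11 and 13: 45 per arm, 50% against 80%, two-sided alpha 0.05. Exact power is the sum over all outcomes (x, y) of Bin(x; 45, 0.8) × Bin(y; 45, 0.5), counting those with Fisher p ≤ 0.05. The result is **81.5%**, so the stated 80% is met. With 15% loss from 104, 104 × 0.85 = 88.4 remain; at 44 per arm exact power is 80.2%.

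Exact size at 45/45 is 2.7%, 3.2% and 2.6% for common rates of 0.50, 0.65 and 0.80. Fisher's conservatism is mainly discreteness, and it is worst with exactly equal arms. With 45 on placebo and 44 on mirabegron, power is 82.9% and size 3.4-4.0%. The simulated Fisher power below therefore exceeds 81.5%.

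**2. The stratified alternative.** Over strata s, with x₁ₛ passages among n₁ₛ on mirabegron, n₀ₛ on placebo, mₛ passages in total and nₛ subjects:

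CMH = (|Σ(x₁ₛ − n₁ₛmₛ/nₛ)| − c)² / Σ[n₁ₛn₀ₛmₛ(nₛ − mₛ) / (nₛ²(nₛ − 1))]

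Here c = 0 without and c = 0.5 with continuity correction. The statistic is compared with 3.84.

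**3. Assumptions.** The documents give no stratum rates or sizes.
- Overall rates are held at 50% and 80%, with a constant conditional odds ratio.
- The spread is the gap in placebo rate between the best and worst stratum, from 0 to 60 points. A spread of 33 is the width of Section 1's range (80 − 47); with equal strata this corresponds to placebo rates of 33.5, 44.5, 55.5 and 66.5%. Spreads of 40 and 60 have no support in the documents.
- Strata are equal, or 15/10/45/30% of subjects.
- 104 are randomised in blocks of 4 within strata (block size assumed), with 15% independent dropout and 20,000 runs per cell. The Monte Carlo standard error is about √(0.85 × 0.15/20,000) = 0.25 points.

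**4. Power (%).** Differences are taken from the rounded figures.

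| Strata | Spread | Fisher | Chi-square | CMH | CMH corrected | CMH − Fisher | CMH − chi-square |
|---|---|---|---|---|---|---|---|
| Equal | 0 | 83.2 | 86.2 | 85.5 | 79.6 | 2.3 | −0.7 |
| Equal | 20 | 82.6 | 85.8 | 85.9 | 79.8 | 3.3 | 0.1 |
| Equal | 33 | 83.1 | 86.4 | 87.1 | 81.2 | 4.0 | 0.7 |
| Equal | 40 | 83.1 | 86.3 | 87.8 | 82.0 | 4.7 | 1.5 |
| Equal | 60 | 84.6 | 87.7 | 91.3 | 86.1 | 6.7 | 3.6 |
| Unequal | 0 | 83.0 | 85.9 | 85.3 | 79.3 | 2.3 | −0.6 |
| Unequal | 20 | 82.4 | 85.6 | 85.5 | 79.5 | 3.1 | −0.1 |
| Unequal | 33 | 82.9 | 86.1 | 86.5 | 80.4 | 3.6 | 0.4 |
| Unequal | 40 | 82.7 | 85.7 | 86.5 | 80.9 | 3.8 | 0.8 |
| Unequal | 60 | 84.0 | 87.2 | 89.8 | 84.2 | 5.8 | 2.6 |

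Type I error: Fisher 2.8-3.5% for spreads of 0-40 and 2.1-2.4% at 60; uncorrected CMH 4.8-5.2% throughout.

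A second set-up (N = 90, no dropout, stratum odds ratios for size/location from 1/1 to 4/3, 40,000 runs) gives the same picture. Fisher to CMH rises from 82.6 to 86.1% at the weak end and from 84.1 to 90.6% at the strong end, that is by 3.5 to 6.5 points. Stratifying alone accounts for −0.4 to +2.4 of these.

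**5. Does the p<0.05 screen bring the strata in?** Logistic model with treatment, size and location only; size effect assumed twice the location effect; 10,000 runs per cell.

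| Spread | Both kept, equal / unequal strata | Neither kept, equal / unequal strata |
|---|---|---|
| 33 | 7.6% / 4.9% | 45.3% / 58.4% |
| 40 | 13.4% / 9.6% | 29.8% / 44.1% |
| 60 | 44.3% / 33.9% | 3.2% / 11.7% |

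At spreads of 33-40 at least one real factor is dropped in 87-95% of trials (100 − 13.4 and 100 − 4.9).

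**6. The adjusted odds ratio.** The marginal value is (0.8/0.2)/(0.5/0.5) = 4.0. The conditional value at spreads of 33/40/60 is 4.32/4.49/5.37 with equal strata and 4.23/4.34/4.82 with unequal strata. With both factors forced in, coverage of the 95% interval for the conditional odds ratio is 94.8-95.5% and Wald type I error is 4.9-5.5%.

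**The case against.** The strongest reply is that nothing is broken. Sizing and analysis name the same test, the test meets its power, and an exact test with about 90 subjects is a defensible choice that guarantees type I control. This stands, and is why the point is an improvement and not a correction.

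Second, most of the power gain has little to do with strata. For spreads up to 40, stratifying itself moves power by −0.7 to +1.5 points; an unstratified chi-square would collect most of the rest. This also stands. The recommended test still delivers the whole gain, and it beats Fisher by 2.3 points even when the strata are not prognostic.

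Third, the 33-point anchor is weak. Section 1's range is general background, while this trial takes only 4-10 mm stones and splits them at 5 mm, so the true spread could be smaller. At 20 points stratifying adds −0.1 to +0.1.

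Fourth, Section 13's multiple logistic model could include both factors. It could, but only through the screen. The retention figures do rest on the assumed 2:1 effect ratio and on a three-term model, whereas the plan leaves its covariate list open.

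None of this touches the gap in estimation: the plan does not say whether its treatment odds ratio is adjusted for the stratification factors.

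**Conclusion.** The concern holds as an efficiency and specification point that the sponsor should act on. Under the assumed stratum effects, an uncorrected CMH test gains about 2 to 5 points of power over Fisher for spreads up to 40, and about 6 to 7 at the unsupported spread of 60, with type I error near 5%. The direction against Fisher is the same in every scenario; the size depends on stratum rates that the documents do not give. The firmer reason to act is that no adjusted treatment estimate is assured, and the significance screen is a poor substitute. Validity here means type I error under the stratified randomisation, not other parts of the plan such as missing primary outcomes.

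**What to change.** In Sections 11 and 13:
- Make the primary test a CMH test stratified by stone size and location as defined in Section 8, and state that no continuity correction is used.
- Report the treatment odds ratio from a logistic model that always contains both factors. Label it conditional, and name a penalised-likelihood fallback for non-convergence.
- Keep Fisher's test as a sensitivity analysis and 45 per arm as the target.

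If guaranteed type I control is preferred, keep Fisher as primary and make one change: force both factors into the odds ratio model.

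The change is wording only, to be made before unblinding. Both factors are known at randomisation, so no new data are needed. It has three costs:
1. Type I error is controlled asymptotically, not guaranteed.
2. The correction must be fixed in advance: a corrected CMH has less power than Fisher at every spread up to 40 (79.3-82.0% against 82.4-83.2%).
3. The conditional odds ratio is not the marginal 4.0, and readers must be told so. Ordinary logistic fitting failed in 0-1% of runs for spreads up to 40, and in 5% at 60 with unequal strata.
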